### 7.11.2 Patient Reported Outcome – TSS at End of Study Treatment

The average of TSS score at the end of study treatment is calculated as per the 1st Secondary Endpoint (Section 5.2). ANCOVA will be applied with treatment as factor, and baseline value and randomization stratum as covariates. The order of the analysis follows the hierarchy definded in Section 6.8.

## 7.12 Analysis of Exploratory Endpoints

- Change in [REDACTED] will be analyzed using [REDACTED] as described below. Only the [REDACTED] collected prior to study drug dosing will be included in the model. The [REDACTED] model includes treatment, week, treatment-by-week interaction as fixed factors, and baseline as covariates. Subject will be the repeated measure factor. The covariance matrix for the repeated measurements will take the form of Toeplitz (TOEP). If the computation does not converge, it will be reduced to the first order autoregressive [AR(1)] followed by compound symmetry (CS). The weekly change scores from Week 1 up to Week 14 will be included in the model.
- Change from baseline in the [REDACTED] scores averaged over the 14 daily scores starting with the day of the last dose to the day before the end of study biopsy. (See 1st Secondary Endpoint for the calculation of average.) For patients whose biopsy is collected prior to Day 99 due to early discontinuation, the average of the last 14 days of

scores recorded for that patient will be used for the analysis will be analyzed using the same method as for the [REDACTED] and TSS scores.

- The average of [REDACTED] scores at the end of study treatment is calculated as per the 1st Secondary Endpoint (Section 5.2). [REDACTED] will be applied with treatment as factor, and baseline value and randomization stratum as covariates.
- Percent Change in the number of [REDACTED] in patients with [REDACTED] will be analyzed using the same method as for the primary efficacy endpoint (see Section 7.10.1).
- Proportions of EG, EGE, and EoE patients with average [REDACTED] per HPF (EG and EGE) or [REDACTED] per HPF (EoE) from [REDACTED] will be analyzed using the same method as the sensitivity analysis for the primary efficacy endpoint (see Section 7.10.3).
- [REDACTED]  
[REDACTED] (respectively) will be summarized at baseline and Week 14 (Day 99).
- Changes in the number of [REDACTED] separately in [REDACTED] [REDACTED] may be analyzed using [REDACTED] similarly to the primary endpoint analysis if sample sizes allow.
- Change from baseline in the scoring of [REDACTED] will be summarized descriptively using mean, SD, and median. Individual assessments will be summarized using frequency tables
- Changes from baseline in the [REDACTED] domain and summary scores will be analyzed similarly to the PRO TSS scores. Instead of using the weekly score, the analysis will be based on the [REDACTED] item scores collected at each visit. The computation of the domain scores and summary scores will be provided by the Optum PRO CoRE software.
- Change from baseline in the [REDACTED] for EoE patients will be summarized.
- Percent changes from baseline in [REDACTED] for averages of Weeks 13-14, 11-14, and Weeks 9-14, and separately for each individual week will be summarized. Baseline for each of the symptom scores is defined the average of all scores for that symptom prior to the first dose of the study drug. The postbaseline weekly [REDACTED] and their percent changes will be summarized for each treatment group everyweek. The weekly percent changes will be analyzed using the [REDACTED] model as described in the analysis for the peripheral eosinophil counts. The comparison between the active dose and placebo

groups for averages of Weeks 13-14, 11-14, and 9-14 will be based on the averages of the least squares means for the corresponding weeks using simple contrasts. The comparison for each individual week will be carried out similarly. P-values and confidence intervals will be presented without multiplicity adjustment.

```
PROC MIXED DATA=XXXX ;
  CLASS TRTP USUBJID WEEK;
  MODEL PCHG = BASE TRTP WEEK TRTP*WEEK / DDFM=KR ;
  REPEATED WEEK / SUBJECT=USUBJID(TRTP) TYPE=TOEP ;
  ESTIMATE "GRP1-GRP3 @ W9-14Avg" TRTP 6 0 -6
    TRTP* WEEK 0 0 0 0 0 0 0 0 1 1 1 1 1 1
    0 0 0 0 0 0 0 0 0 0 0 0 0 0 0
    0 0 0 0 0 0 0 0 -1 -1 -1 -1 -1 -1
    / CL DIVISOR=6;
  ESTIMATE "GRP2-GRP3 @ W13-14Avg" TRTP 0 2 -2
    TRTP* WEEK 0 0 0 0 0 0 0 0 0 0 0 0 0 0 0
    0 0 0 0 0 0 0 0 0 0 0 0 0 0 1 1
    0 0 0 0 0 0 0 0 0 0 0 0 0 0 0 -1 -1
    / CL DIVISOR=2;
  ESTIMATE "GRP1-GRP3 @W1" TRTP 1 0 -1
    TRTP* WEEK 1 0 0 0 0 0 0 0 0 0 0 0 0 0 0
    0 0 0 0 0 0 0 0 0 0 0 0 0 0 0 0
    -1 0 0 0 0 0 0 0 0 0 0 0 0 0 0 0
    / CL;
RUN ;
```

- Changes from baseline in the [REDACTED] for averages of Weeks 13-14, 11-14 and Weeks 9-14 and separately for each individual week will be analyzed in the same way as for the percent change from baseline.
- Change from baseline in [REDACTED] will be analyzed using MMRM similarly as described for and [REDACTED] and TSS scores.
- [REDACTED] will be summarized at baseline and Week 14 using geometric mean, coefficient of variation, median, and minimum and maximum.
- Subject counts at each [REDACTED] at Day 99 will be tabulated.

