#### **3.2.3 Methods of Assigning Subjects to Treatment Group**

Approximately 60 subjects will be stratified based on the highest weekly average of the qualifying symptom of disease recorded on the PRO questionnaire during the screening period (PRO score 3–4.9, or 5.0–10.0) and randomized in a 1:1:1 ratio to Treatment Groups 1, 2, and 3 (Section 3.2.1).

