## 6.3 Adjustment for Covariates

Baseline and randomization stratum may be adjusted, where appropriate, in estimating the between group difference using ANCOVA, MMRM, or Cochran-Mantel-Haenszel tests.

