## 7.10 Analysis of Primary Efficacy Endpoint

### 7.10.1 Primary Analysis of Primary Efficacy Endpoint

The primary efficacy endpoint is the percent change from baseline to Day 99 in the number of eosinophils per HPF in gastric or duodenal mucosa with biopsy. For subjects who provide gastric or duodenal only biopsy, the calculation will be based on the average count of the highest readings from the respective mucosa at baseline and Day 99. For subjects who provide both gastric and duodenal biopsies, the calculation will be based on the average count of the highest readings from the Day 99 biopsy that correspond in location (gastric or duodenal) to the location with the highest average count at baseline. This endpoint will be summarized by treatment group.

The pooled high/low dose group and each active dose group will be compared to the placebo group in pairwise comparison using analysis of covariance (ANCOVA) model with percent change from baseline as outcome, treatment as factor, and baseline value and randomization stratum as covariates. To control for the type-I error, the Gatekeeping procedure defined in Section 6.8 will be followed.

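### The exploratory repeated-measures model omits the randomisation stratum that the other efficacy models adjust for; its comparisons are somewhat conservative if the stratum is prognostic beyond baseline.

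*SAP*

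**What the plan says.** Section 3.2.3 states that subjects are "stratified based on the highest weekly average of the qualifying symptom of disease recorded on the PRO questionnaire during the screening period", in two levels (3–4.9 and 5.0–10.0), and "randomized in a 1:1:1 ratio to Treatment Groups 1, 2, and 3".

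The stratum then enters most efficacy analyses:

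- The primary ANCOVA (7.10.1) has "treatment as factor, and baseline value and randomization stratum as covariates".
- The CMH test (7.10.2) is stratified by it.
- The logistic model (7.10.3) includes it, and 7.11.1 uses a similar model for the responder endpoint.
- The TSS ANCOVA (7.11.2) includes it.
- One exploratory end-of-treatment score in 7.12 is also modelled with baseline and stratum.

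The repeated-measures model in 7.12 differs. Its text says the "model includes treatment, week, treatment-by-week interaction as fixed factors, and baseline as covariates". The PROC MIXED code agrees: the class variables are "CLASS TRTP USUBJID WEEK" and the model line is "MODEL PCHG = BASE TRTP WEEK TRTP*WEEK / DDFM=KR". No reason is given for leaving the stratum out.

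The general rule in 6.3 reads "Baseline and randomization stratum may be adjusted, where appropriate, in estimating the between group difference using ANCOVA, MMRM, or Cochran-Mantel-Haenszel tests".

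**The concern.** When randomisation is stratified, the arms are balanced on the stratum by design. If the stratum also predicts outcome, that balance removes a source of variation from the treatment comparison. A model without the stratum leaves this variation in its residual term. Its reported standard error then exceeds the true sampling error, its confidence intervals are too wide, and its tests reject less often than their nominal level.

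At stake are the weekly symptom comparisons and the averages over Weeks 9-14, 11-14 and 13-14, together with the other exploratory endpoints that borrow this model. The plan also leaves the reader without a reason why one class of model departs from the covariate set used elsewhere.

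**Working it through.** **Inputs from the SAP.** Section 3.2.3 gives about 60 subjects, 1:1:1 (so 20 per arm), and two strata. The model terms are those of 7.12. For symptom scores, the baseline covariate is the mean of all pre-dose scores for that symptom (7.12).

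**Input not in the SAP.** The partial R-squared of the stratum, given treatment and baseline, is assumed to lie between 0 and 0.20.

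**The plan's own figure.** The SAP states no standard error or power for the repeated-measures analyses. Its only power figure is for the primary endpoint (3.5): difference 20 points, SD 20, 20 per group, alpha 0.05, 87%. A two-sided two-sample t-test has noncentrality 20 / (20 × √(2/20)) = 3.16 on 38 df and gives 86.9%, so the figure reproduces. It does not bear on the stratum question.

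**Step 1: formula.** For a between-subject contrast with 60 subjects, the model with intercept, two treatment terms and baseline leaves 60 − 4 = 56 df. Adding the stratum leaves 55. With arms balanced on the stratum,

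SE with / SE without = √((1 − R²) × 56/55).

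Break-even is at R² = 1 − 55/56 = 0.018.

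| Assumed partial R² | SE with / without | SE without, relative to with |
|---|---|---|
| 0 | 1.009 | 0.9% smaller |
| 0.01 | 1.004 | 0.4% smaller |
| 0.02 | 0.999 | 0.1% larger |
| 0.05 | 0.984 | 1.7% larger |
| 0.10 | 0.957 | 4.5% larger |
| 0.20 | 0.903 | 10.8% larger |

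**Step 2: simulation with baseline and stratum from the same diary.** There were 4,000 trials per setting, with 60 subjects and permuted blocks of 3 within stratum. Assumed inputs were four weekly screening means per subject (subject mean 5, between-subject SD 1.5, weekly SD 0.8), stratum = highest week at or above 5, baseline = mean of the four weeks, a baseline slope of −5 per point, residual SD 20 and no treatment effect. Stratum and baseline correlated at about 0.74.

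| Stratum effect beyond baseline | Mean SE without | Mean SE with | SE without, relative to with | Trials where adding the stratum lowered the SE |
|---|---|---|---|---|
| 0 | 6.332 | 6.367 | 0.5% smaller | 24% |
| 5 points (0.25 SD) | 6.348 | 6.364 | 0.3% smaller | 30% |
| 10 points (0.5 SD) | 6.389 | 6.345 | 0.7% larger | 49% |
| 20 points (1 SD) | 6.626 | 6.359 | 4.2% larger | 85% |

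Mean treatment estimates without and with the stratum were nearly identical (for example −0.149 and −0.156 at 0.5 SD), so the omission adds no material bias.

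**Step 3: calibration of the reported SE.** A second simulation (4,000 trials per setting, 20 per arm, residual SD 1) compared the mean model SE with the empirical SD of the estimate.

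- Stratum effect 0.5 SD: without the stratum 0.325 against 0.318 (2.2% too large); with it 0.318 against 0.317. The 5% test without the stratum rejected 4.7% under the null.
- Stratum effect 0.8 SD: without the stratum 0.338 against 0.321 (5.3% too large); with it 0.318 against 0.318. The 5% test without the stratum rejected 4.0%.

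The first SE is close to √(1 + 0.25 × 0.5²) × √(2/20) = 0.326, the value for an evenly split stratum unrelated to baseline. These figures therefore suit a case with little overlap between the two, and Step 2 the case with strong overlap. The true precision of the estimate changed little here: 0.318 against 0.317 and 0.321 against 0.318, or 0.3% and 0.9%. The main effect is an overstated SE.

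**Limits.** All simulations use subject-level averages, which equal the repeated-measures contrast only with complete data. The per-protocol set may also be smaller than 60.

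**The case against.** The strongest reply is that nothing in the plan is violated. Section 6.3 makes stratum adjustment optional, and the 7.12 text and code agree with each other. That stands: a reader might infer that the model contradicts 6.3, but the wording there is permissive.

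A reader might also infer that the standard errors are certainly larger than they need to be. The document does not support that. It gives no information on how prognostic the stratum is once baseline is in the model, and below a partial R² of about 0.018 adding the term makes the SE slightly larger. For peripheral eosinophil counts, which use the same model, a symptom-severity stratum need not be prognostic at all.

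A third inference would be that the omission makes the weekly results non-comparable with the TSS ANCOVA. Those analyses already differ. The ANCOVA uses a window of 14 daily scores before the biopsy with a roll-back rule (5.2), while the weekly analyses use study weeks with their own missing-data rules (Table 2, 6.4). In a linear model of a randomised comparison, dropping the stratum does not change which treatment contrast is estimated.

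What remains is an unexplained departure from the stratified design and from the covariate set of the other efficacy models. Optional wording in 6.3 does not supply a reason for it.

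**Conclusion.** The point holds as a low-cost improvement. The repeated-measures model leaves out a factor the trial randomises by and most other efficacy models adjust for. If that factor is prognostic beyond baseline, the exploratory comparisons are somewhat conservative.

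The 1%-smaller to 11%-larger range in standard error rests entirely on the assumed partial R² of 0 to 0.20. A difference within a few percent is the likely outcome for symptom scores, because baseline and stratum share the screening diary. The overlap may be weaker where a score is not the qualifying symptom, since the stratum is built on that symptom and baseline on each score's own mean.

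The comparisons concerned are exploratory and reported without multiplicity adjustment. None belongs to the testing hierarchy in 6.8, so no primary or secondary conclusion depends on this.

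**What to change.** Add the randomisation stratum to the CLASS statement and to the model line, `MODEL PCHG = BASE STRATUM TRTP WEEK TRTP*WEEK`, keeping the existing degrees-of-freedom option. Add it to the model description in the first bullet of 7.12. Use one variable name throughout; the sample code calls it RANDSTRA in 7.10.2 and stratum in 7.10.3. The treatment contrasts need no stratum coefficient, because an additive stratum term cancels between arms.

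The cost is one term in the code, one degree of freedom, and a standard error up to about 1% larger if the stratum adds nothing beyond baseline. If the sponsor prefers to leave the term out for some endpoints, one sentence in 7.12 giving the reason would settle the matter before unblinding.

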### 7.13 Analysis of Pharmacokinetic Endpoint

Serum concentrations of AK002 will be summarized for each treatment group by study visit.

## 7.14 Safety Analyses

### 7.14.1 Adverse Events

Safety assessments will be based mainly on the nature, frequency, relationship, and severity of adverse events (AEs). AEs will be coded by primary system organ class (SOC) and preferred term (PT) according to the Medical Dictionary for Regulatory Activities (MedDRA) version 21.0. The treatment-emergent adverse events (TEAEs) will be summarized by the number and percentage (n and %) of subjects in each SOC and PT. For summaries by relationship to study drug, “possibly related” will be combined with “related”, and “unlikely/remotely related” will be combined with “not related.” When multiple AEs are reported with the same PT, the AE of the strongest relation will be included in summary by relationship, and the AE of the most severe grade will be included in the summary by severity table.

The following AE incidence tables will be presented.

- Overview of TEAEs to include
  - Number (%) of patients who reported at least one TEAE
  - Number (%) of patients who reported at least one treatment-related TEAE
  - Number (%) of patients who reported at least one severe TEAE
  - Number (%) of patients who reported at least one serious TEAE
  - Number (%) of patients who reported at least one TEAE leading to treatment discontinuation
  - Number (%) of patients who died on study
- TEAEs by PT sorted by decreasing order of subject incidence in the combined treatment group
- TEAEs by SOC and PT in alphabetical order
- TEAEs by SOC, PT, and maximum severity
- TEAEs by SOC, PT, and strongest relationship to study drug
- TEAEs leading to withdrawal by SOC and PT, if warranted by sample size
- Serious TEAEs by SOC and PT, if warranted by sample size

All AEs will be listed with onset/stop day, relationship to study drug, severity, action taken, and outcome. Pertinent subject information including treatment group and demographics will also be included.

Separate listings will be provided for TEAEs leading to study discontinuation, TEAEs of special interest, and Treatment-emergent serious AEs (TESAEs).

#### **7.14.2 Laboratory Test**

Laboratory data will be summarized by presenting summary statistics of raw data and change from baseline values (means, medians, standard deviations, ranges). For quantitative laboratory parameters, both actual values and change from baseline values will be summarized.

Shift tables will be presented, in which, lab test results at baseline and post-baseline will be classified into below ( $<\text{LLN}$ ), within ( $\geq\text{LLN}$  and  $\leq\text{ULN}$ ), and above ( $>\text{ULN}$ ) normal ranges. Subject incidences (n and %) will be presented for the shift from baseline to the post-baseline visits.

Note the summary and shift tables will only use the planned/scheduled tests. However, both scheduled and unscheduled/repeat tests will be included in the data listing.

A complete laboratory data listing, including hematology, biochemistry, urinalysis, and Anti-Drug-Antibodies (ADA) will be provided for all subjects.

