## 3. Study Design

### 3.1 General Description

This is a Phase 2, multi-center, randomized, double-blind, placebo-controlled study. The study comprises a screening period of 21 to 35 days with baseline evaluations for study eligibility. If subjects meet histology and symptom eligibility criteria, they will receive 4 doses of AK002 or placebo by IV infusion on Days 1, 29, 57, and 85. Subjects will be followed for 56 days after last dose. Follow-up visits will occur on Days 113 and 141.

If the absolute lymphocyte or eosinophil counts have not recovered by Day 141, the follow-up period will be extended, and subjects will be followed until the counts have recovered. During the extended follow-up period, subjects will return to the site every 28 days for a follow-up safety visit.

Total study duration will be up to approximately 23–25 weeks.

The study design is presented schematically in [Table 1](#).

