- 21) Blood for CBC with differential, including absolute [REDACTED] and basophil counts, will be obtained just prior to each infusion, 1 hour after the end of each infusion, 4 hours after the end of infusion 1, as well as during the screening period and on Days 4, 15, 99, 113, and 141 or ET and Extended Follow-Up, if applicable. All differential blood counts from Day 1 (post-dose) and prior to Day 141 or Early Termination will be blinded to the Sponsor and the site. An unscheduled CBC may be collected at the request of the unblinded safety monitor. Differential blood counts will not be blinded at the Day 141/ET visit and these results will be used by the site to determine if the subject needs to enter the Extended Follow-Up period.
- 22) Blood for chemistry will be obtained pre-dose on dosing Days 1, 29, 57, and 85, as well as during the screening period and on Day 15, Day 113, and Day 141 or ET.
- 23) Urine for standard urinalysis will be obtained pre-dose on dosing Days 1, 29, 57, and 85, as well as during the screening period and on Day 113 and Day 141 or ET.
- 24) Serology will include HBsAg, hepatitis C antibody, anti-HBc, and HIV.
- 25) If an Infusion-related reaction causes an infusion interruption or cessation a sample of blood should be obtained for exploratory safety analysis within 1–2 hours of the onset of the symptoms. A sample of blood should be obtained for testing of histamine and tryptase levels within 1–2 hours, if anaphylaxis is suspected.
- 26) Blood for PK should be obtained pre-dose on dosing Days 29, 57, and 85, as well as during screening and on Days 15, 113, and 141 or ET.
- 27) Blood samples for exploratory analysis will be collected pre-dose on Days 1, 29, and 85 and also on Day 141 or ET.
- 28) Blood samples for ADA will be collected during the screening period, on Days 15, 29, 57, 85 and Day 141 or ET and anytime an immunogenicity-related AE occurs.
- 29) Blood samples for Total Serum IgE will be collected on Day 1 and on Day 141 or ET.
- 30) The ET Visit should be conducted 28 ( $\pm 3$ ) days after the last dose of study drug or prior to this, if necessary, to ensure compliance with the visit. If early termination occurs more than 28 days after the last dose of study drug, then perform the ET visit as soon as possible. The procedures listed under the final follow-up visit will be conducted unless directed otherwise by the Medical Monitor.

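### No laboratory table in SAP 7.14.2 includes unscheduled blood counts, each subject's worst post-baseline lymphocyte count, or the number of subjects who were ever low

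*SAP*

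**What the plan says.** Section 7.14.2 plans three laboratory outputs.

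- **Summaries:** "summary statistics of raw data and change from baseline values (means, medians, standard deviations, ranges").
- **Shift tables:** "lab test results at baseline and post-baseline will be classified into below", within or above the normal range, and "Subject incidences (n and %) will be presented for the shift from baseline to the post-baseline visits".
- **Listing:** complete for all subjects.

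The data rule is "Note the summary and shift tables will only use the planned/scheduled tests". It is followed by "However, both scheduled and unscheduled/repeat tests will be included in the data listing".

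Note 21 to Table 1 sets the CBC schedule. On dosing days blood "will be obtained just prior to each infusion, 1 hour after the end of each infusion, 4 hours after the end of infusion 1". Samples are also due at screening, on Days 4, 15, 99 and 113, at Day 141 or early termination, and in any extended follow-up. The same note adds "An unscheduled CBC may be collected at the request of the unblinded safety monitor". It blinds site and sponsor to all differentials after the first dose and before Day 141 or early termination.

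Section 3.1 shows that these counts matter to the safety plan: "If the absolute lymphocyte or eosinophil counts have not recovered by Day 141, the follow-up period will be extended".

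**The concern.** Lymphocyte and eosinophil counts are the only laboratory values whose non-recovery lengthens follow-up, and Section 2.4 makes laboratory change part of the safety objective. A reader of the study report will want to know how many subjects in each arm had a low lymphocyte count at any time, and how low it went. The planned tables do not answer either question directly.

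- Unscheduled results are in no table.
- Visit columns cannot be added up to a number of subjects ever low.
- A single class below the lower limit of normal (LLN) puts a marginal and a deep fall in the same cell.

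For most laboratory tests, adverse event reports would partly make up for this. Here they do so less well, because the sites do not see the on-treatment differentials. Subjects who move to the extension at Day 113 skip Day 141 (note 33), so unless they terminate early they have no unblinded post-dose differential under this protocol.

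**Working it through.** The plan states no figure on this point, so there is none to reproduce. The check has two parts.

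**1. Where a low lymphocyte count goes**

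| Where it occurs | Visit summary and shift table | Subject's worst value or ever-low count | Listing |
|---|---|---|---|
| Scheduled time point | Yes (7.14.2) | Not tabulated | Yes |
| Unscheduled or repeat test | No (7.14.2) | Not tabulated | Yes |
| Extended follow-up | Outside the data lock for the final analysis (6.6) | Not tabulated | Outside that lock |

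A low count reported as an adverse event can also enter the tables of Section 7.14.1. CTCAE appears in the abbreviation list, but no section uses it to grade laboratory values. Section 7.14.2 also does not say which reading stands for a dosing visit that has both pre-dose and post-infusion samples. Section 7.14.3, by contrast, summarises vital signs by visit and time point.

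**2. How far a by-visit share can lie from an ever-low share**

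Scheduled CBC time points after the first dose, from note 21:

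- Day 1, 1 h and 4 h after infusion: 2
- Days 4 and 15: 2
- Days 29, 57 and 85, pre-dose and 1 h after infusion: 3 × 2 = 6
- Days 99, 113 and 141 (or early termination): 3
- Total: 2 + 2 + 6 + 3 = 13

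The SAP gives no rate of low counts. Let p be an assumed probability of a value below LLN at each time point, and rho an assumed within-subject correlation.

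- Independent: P(ever low) = 1 − (1 − p)^13. At p = 0.05 this is 1 − 0.95^13 = 0.487.
- Correlated (beta-binomial): a = p(1/rho − 1), b = (1 − p)(1/rho − 1), and P(ever low) = 1 − B(a, b + 13)/B(a, b), where B is the beta function.

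| p per time point | Independent | rho 0.2 | rho 0.5 | rho 0.8 |
|---|---|---|---|---|
| 2% | 23% | 12% | 6% | 3% |
| 5% | 49% | 27% | 15% | 8% |
| 10% | 75% | 47% | 28% | 16% |

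Over this grid the ever-low share is between 0.161/0.10 = 1.6 and 0.231/0.02 = 11.5 times the share at a single time point. Repeated counts in one person are correlated, so the independent column is an upper reference and not an expectation. The direction does not depend on the assumptions: among the same subjects, the ever-low share cannot be below the share at any one visit.

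These figures cover scheduled tests only. The effect of leaving out unscheduled tests cannot be computed, because the SAP does not say how often they occur. For scale, Section 3.5 has 20 subjects per group, so one subject is 1/20 = 5 percentage points of an arm.

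**The case against.** The case for the plan as written has real substance.

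- **Unequal ascertainment.** The person who requests extra CBCs knows the treatment arm. Mixing those results into a between-arm table gives some subjects more chances of an extreme value, and not at random. This stands. It is a good reason to keep the scheduled-only tables and to show any worst-value table both ways. It does not justify having no worst-value table.
- **Depth is partly shown.** The summaries include ranges, so the lowest scheduled count in a group appears. This also stands. A group minimum is one value, however, and does not say how many subjects were deeply low.
- **The rule is clear and the trial is small.** About 60 subjects are planned and every result is listed. This is true, but a listing does not compare arms.

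Four stronger readings are tempting and are not supported.

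- A reader might infer that a subject's worst lymphocyte count reaches no safety table at all. If it falls at a scheduled time point, it enters that visit's range and shift cell. It is only not identified as the subject's worst or graded.
- A reader might infer that the tables are biased in favour of the drug. The SAP does not say why the monitor would request a test, how often, or in which arm.
- A reader might infer that adverse event tables cannot capture lymphopenia. The safety monitor is unblinded and could pass on a concern, a clinical consequence could be reported, and events of special interest are listed. Blinding narrows this route without closing it, and it removes no data from the final laboratory tables. Day 113 counts of subjects who roll over are still tabulated.
- A reader who counts CBC days instead of samples gets 9 and, at 5% with independence, 1 − 0.95^9 = 37%. That omits the extra samples on dosing days and ignores correlation, so it should not be quoted as an estimate.

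**Conclusion.** The point holds as a gap in reporting. Section 7.14.2 plans no laboratory table that includes unscheduled CBCs, gives each subject's worst post-baseline lymphocyte count, or counts subjects ever low. That the shift tables are by visit is explicit; that the summary statistics are too is a reasonable reading.

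The size is unknown. The 49%, 15% and 8% (independence, correlation 0.5 and 0.8) rest on an assumed 5% at each of 13 time points and show only how far apart the two kinds of share can be. Nothing in the SAP shows that the omission favours an arm. No planned figure or test changes. This is an inexpensive improvement to the safety tables and does not correct an error in the efficacy analysis.

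**What to change.** In Section 7.14.2, keep the scheduled-only by-visit tables and add the following by arm:

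1. A shift table from baseline to each subject's worst post-baseline value, using all scheduled results (post-infusion samples included) and all unscheduled or repeat results.
2. Each subject's minimum post-baseline lymphocyte and neutrophil count in graded classes, for example CTCAE grades, with the number and percentage of subjects in each class.
3. Items 1 and 2 repeated on scheduled tests only, with a footnote that unscheduled tests may be requested by someone who knows the arm.

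Also state which reading represents a dosing visit in the by-visit tables, or tabulate by time point as Section 7.14.3 does for vital signs.

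The cost is a few lines of SAP text and a few tables from data already collected. The small downside is that subjects with more unscheduled tests have more chances of an extreme value. Item 3 makes this visible.
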